2.4 Later phases of the project

The second phase is to invite oncologists across the West Midlands, many of whom have already expressed an interest, to join the study and to send the researchers anonymised, linked patient data and that from the Tool.

The third phase is to make the Tool available, free of charge, as an app on both the Android Store and the Apple App Store. This will allow patients to self-monitor aspects of their health and to share this as they wish with their clinician. Users will be asked to evaluate the app by the usual means on their app store.

Clinicians who choose to use it with their patients will be asked to share with the researchers anonymised, linked patient data and that from the Tool.

The target group for this research consists of anyone being treated for advanced and metastatic prostate cancer and their clinician/s. It does not involve persons under 18 years of age nor persons from a potentially vulnerable group.

2.5 How the data will be analysed

Quantitative data will be analysed by means of statistical tests such as Mann Whitney-U, Spearman Rank Correlation etc. using SPSS v.26. Qualitative data will be analysed using thematic analysis and the constant comparative method.

2.6 The ethical considerations involved in this project.

Patients and clinicians will be asked if they wish to opt into the study and be required to give their explicit consent, both for sharing data and, if they accept to volunteer, for interviews.

All patient data will be anonymised prior to its being shared with the researchers. Recording and notes of interviews will be anonymised. Only the research team will have access to any raw data. All data will be held in a manner that prevents any linking of it back to either the patient or their clinician.

All data held will be anonymous and will be held on a secure University or NHS server. Only the research team will have access to any raw data. All data will be held in a manner that prevents any linking of it back to either the patient or their clinician.

Participants will be given a participant information sheet, which will detail the risks and benefits of participating and of their right to refuse participation or withdraw from the research at any time.

2.7 References.

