2.1 The research questions

- To what extent do each of the five items in the WAT correlate to the patient's disease status?
- How do patients and clinicians feel about using the WAT?

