2.3 How the research will be conducted

In the light of the COVID-19 pandemic, oncologists at New Cross Hospital are advised to consider using the Tool (as per the *Oncology Interim Prostate Cancer Patient Management Guidelines* (8)) as a means of home monitoring of patients. The present project intends to provide robust evidence as to the clinical usefulness of Tool as well as insights into the drivers and barriers to its use by patients and clinicians.

This is a mixed-method study, incorporating both quantitative and qualitative elements. As such, it is both objective and subjective:

- a) It is subjective in that, in using the Wolverhampton Assessment Tool, the patient selects his response to each question on the basis of how he *feels* normally
- b) It is objective in that the tools to be used in the analysis of the quantitative data [i.e. statistical tests such as Mann Whitney-U, Spearman Rank Correlation etc.] are independent of the person using them
- c) Determining clinically the patient's disease status employs objective measures such as PSA, size, distribution and type of metastasis, frequency of night-time urination etc. as well as the clinician's professional judgment which contains both objective and subjective elements (9, 10)
- d) The researchers are not mirrors but they are rather prisms and hence the entire study from conception to analysis and report is a refraction of their experiences

The first phase of the research is a full pilot of the Wolverhampton Assessment Tool in New Cross Hospital, Wolverhampton. Patients who agree to use the Tool to self-monitor their aspects of their health will be invited to consent to share with the researchers their anonymised data from the Tool as well as linked, anonymised clinical data. The frequency of collection of data will be at the discretion of the clinician. Participating patients and clinicians will be invited to take part in a short, semi-structured interview on their experience of using the Tool. All patient data will be treated anonymously, and none linked back to the patient or to their clinician/s.

Clinicians will be asked to record any reasons given by patients who decline to use the Tool.

The clinical data sought on patients will include:

- a) Age
- b) Stage of cancer at diagnosis in terms of the primary tumour, and any presence of disease in lymph nodes and bones
- c) Current stage of cancer in terms of the primary tumour, and any presence of disease in lymph nodes and bones

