2.8 Appendix

Name
Hospital No.....
Address.....
Patient Label.

Clinical Assessment Tool

Please score your pain ticking the one number that represents your pain normally	0 none	1	2	3	4	5	6	7	8	9	10 As bad as I can imagine
Comment:											
I have problems when I urinate- please tick the number that best represents you normally	0 none	1	2	3	4	5	6	7	8	9	10 As bad as I can imagine
Comment:											
I have problems eating- please tick the number that best represents you normally	0 none	1	2	3	4	5	6	7	8	9	10 As bad as I can imagine
Comment:											
I feel tired- please tick the number that best represents you normally	0 none	1	2	3	4	5	6	7	8	9	10 As bad as I can imagine
Comment:											
Please tick which statement below best represents you normally											
I am fully completing my normal activities											10
I have minor restrictions in strenuous physical activity											9
I am active, but tire more quickly											8
I am experiencing greater restriction of activities and spend less time in work activities											7
I am up and around, but activities are minimal; I keep busy by being involved in quieter activities											6
I am lying around much of the day, but I get dressed; I do no active work but I participate in quiet activities											5
I mainly stay in bed and participates in some quiet activities											4
I stay in bed, needing assistance even for quiet activities											3
I sleep often and limited to very passive activities											2
I don't mobilise and I do not get out of bed											1
Patient is unresponsive											0
Thank you for your time											
Office Use:										Totals	
Date:	Treatment :			Cycle:		Day:

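### The tests named in section 2.5 assume independent rows, but the protocol foresees repeated forms per man in unequal numbers and does not make the man the unit of analysis

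*Protocol*

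**What the plan says.** The first research question (Protocol section 2.1) is one of estimation: "To what extent do each of the five items in the WAT correlate to the patient's disease status".

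Section 2.5 gives the whole quantitative analysis in one sentence: "Quantitative data will be analysed by means of statistical tests such as Mann Whitney-U, Spearman Rank Correlation etc. using SPSS v.26". Section 2.3 names the same two tests as examples. No method for repeated measures and no unit of analysis appears anywhere.

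On data collection, section 2.3 describes the Tool "as a means of home monitoring of patients", invites "Patients who agree to use the Tool to self-monitor their aspects of their health", and states: "The frequency of collection of data will be at the discretion of the clinician". The form in the appendix (section 2.8) has fields for date, treatment, cycle and day. Men are asked to "share with the researchers their anonymised data from the Tool as well as linked, anonymised clinical data". Section 2.6 adds: "All data will be held in a manner that prevents any linking of it back to either the patient or their clinician". No study code for grouping one man's forms is described.

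**The concern.** Sections 2.3 and 2.5 do not fit together as written. A frequency of collection has meaning only if collection recurs, and a form with cycle and day fields suits completion across treatment cycles. One man can therefore supply several forms, and the number will depend on his clinician. Forms from the same man resemble each other, and so do his successive disease-status values. Some status variables, such as stage at diagnosis, do not change at all within a man.

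Spearman's and Mann-Whitney's standard inference counts each form as new, independent information. Run on forms as collected, it would have two consequences:

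- Uncertainty is understated, so chance associations look firmer than they are.
- A man with 12 forms carries 12 times the weight of a man with one. This needs no assumption about correlation.

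Phase 1 is meant to show in principle that the Tool is clinically useful, ahead of a regional phase and an app. Overstated precision bears directly on that.

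**Working it through.** **Inputs.** The protocol gives no sample size, significance level, forms per man or ICC, so there is no figure of its own to reproduce. Every number below is an assumption, chosen to span a plausible range.

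**Formula.** With m forms per man and no true association, the variance of a form-level correlation is inflated by DE = 1 + (m − 1) × ICC(item) × ICC(status). The ratio of true to naive standard error is √DE. The true two-sided error of a nominal 5% test is 2 × [1 − Φ(1.96/√DE)]. The last column is a simulation of form-level Spearman with 50 men, a 0–10 item and 1,000 null studies per setting.

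| Forms per man | ICC item / status | DE | √DE | Error, formula | Error, simulated |
|---|---|---|---|---|---|
| 2 | 0.3 / 0.3 | 1 + 1×0.09 = 1.09 | 1.04 | 6.0% | 6.8% |
| 4 | 0.5 / 0.5 | 1 + 3×0.25 = 1.75 | 1.32 | 13.8% | 12.7% |
| 6 | 0.7 / 0.7 | 1 + 5×0.49 = 3.45 | 1.86 | 29.1% | 30.1% |
| 12 | 0.7 / 0.7 | 1 + 11×0.49 = 6.39 | 2.53 | 43.8% | 41.7% |
| 12 | 0.7 / 1 (status fixed per man) | 1 + 11×0.70 = 8.70 | 2.95 | 50.6% | 51.5% |

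**Unequal numbers.** With 1 to 22 forms per man (mean 6), simulated error was 15.6% (ICCs 0.3), 48.2% (ICCs 0.7) and 55.4% (item 0.7, status fixed). With exactly 6 forms each, the same settings gave 9.5%, 30.1% and 33.9%.

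**Mann-Whitney U** on all forms, with the group fixed per man and item ICC from 0.3 to 0.7, gave 7.8–13.8% (2 forms), 20–35% (6 forms) and 34–55% (12 forms).

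**One value per man.** Error returned to about 5% in every setting: Spearman on patient means 4.2–6.4%, Spearman on the first form 3.9–5.9%, Mann-Whitney on patient means 3.7–6.3%. Simulation error is about ±1.4 points.

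**Does the estimate move?** With 40 men, 1 to 11 forms each unrelated to status, ICCs 0.6 and 0.8 and a between-man correlation of 0.6, pooled rho and man-weighted rho both averaged 0.385. Unequal weight alone therefore did not shift it.

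**Are summaries interchangeable?** No. Take the same ICCs and between-man correlation, with 6 forms each. The form-level product-moment correlation is 0.6 × √(0.6 × 0.8) = 0.42. The reliability of a six-form mean is 0.6/(0.6 + 0.4/6) = 0.90 for the item and 0.8/(0.8 + 0.2/6) = 0.96 for status. The correlation of patient means is then 0.6 × √(0.90 × 0.96) = 0.56. Simulated rank correlations agree: about 0.39 weighted by form, against 0.52 to 0.53 on patient means.

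**The case against.** The strongest reply is that the error is not in the document. The test list is open-ended, and no sentence says that forms will be pooled as independent rows. The unit of analysis is often set in a statistical analysis plan, which may exist here. Both named tests are valid on one value per man, so the tests themselves are not wrong. All of this stands, and it makes the point a risk in the present wording and not a stated error. It does not dispose of the point: both named examples share one assumption, and the data structure in section 2.3 does not meet it unless forms are first reduced or weighted by man. That is a mismatch within the protocol.

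Three stronger readings are tempting, and the documents do not support them:

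- A reader might infer that the intervals would be far too narrow. That depends wholly on assumed forms per man and ICCs. With 2 forms and ICCs of 0.3 the standard error is only 4% too small by ratio.
- A reader might infer that the estimate would mainly describe the men with most forms, and so be biased. It shifts only if form counts are related to disease status or to the strength of association. Clinician discretion makes this possible, but nothing in the protocol shows it.
- A reader might take it as stated that every man completes several forms. It is a strong inference from the monitoring purpose, the discretionary frequency and the form's fields, but no sentence says so.

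The protocol also ties its proof-of-principle aim to no significance threshold. The false-positive rates therefore measure how far uncertainty is understated; they do not predict a wrong decision.

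**Conclusion.** The point holds as a conditional one and should be addressed. If Spearman and Mann-Whitney U are applied to the forms as collected, uncertainty is understated and men are weighted by their number of forms. The true standard error runs from about 1.04 to about 3 times the naive one, and the real error of a nominal 5% test from about 6% to about 50%. These ranges rest on 2 to 12 forms per man and ICCs from 0.3 up to a status fixed within each man, none of which comes from the documents. If each man supplies only one form, there is no inflation.

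**What to change.** Amend section 2.5 to make the man the unit of analysis:

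- **Estimate.** Keep Spearman's rho between each item and the disease status dated nearest to that form. Weight each form by 1 over that man's number of forms, so that each man has total weight 1.
- **Interval.** Take 95% confidence intervals from a bootstrap that resamples men with all their forms, within hospital in phase 2. This procedure was not itself simulated here; the check above covers one value per man.
- **Mann-Whitney U.** Run it only on one pre-stated value per man.
- **Patient means.** Do not offer them as an equivalent alternative to the weighted rho. They estimate a different, larger correlation.
- **Study code.** Provide in section 2.6 for a non-identifying code that groups one man's forms. This is compatible with not tracing data back to him.

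The cost is a few sentences, a short bootstrap script, the study code and wider intervals. Changing the wording before data are analysed avoids having to choose the unit after seeing results.

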2.8 Appendix

Name
Hospital No.....
Address.....
Patient Label.

Clinical Assessment Tool

Please score your pain ticking the one number that represents your pain normally	0 none	1	2	3	4	5	6	7	8	9	10 As bad as I can imagine
Comment:											
I have problems when I urinate- please tick the number that best represents you normally	0 none	1	2	3	4	5	6	7	8	9	10 As bad as I can imagine
Comment:											
I have problems eating- please tick the number that best represents you normally	0 none	1	2	3	4	5	6	7	8	9	10 As bad as I can imagine
Comment:											
I feel tired- please tick the number that best represents you normally	0 none	1	2	3	4	5	6	7	8	9	10 As bad as I can imagine
Comment:											
Please tick which statement below best represents you normally											
I am fully completing my normal activities											10
I have minor restrictions in strenuous physical activity											9
I am active, but tire more quickly											8
I am experiencing greater restriction of activities and spend less time in work activities											7
I am up and around, but activities are minimal; I keep busy by being involved in quieter activities											6
I am lying around much of the day, but I get dressed; I do no active work but I participate in quiet activities											5
I mainly stay in bed and participates in some quiet activities											4
I stay in bed, needing assistance even for quiet activities											3
I sleep often and limited to very passive activities											2
I don't mobilise and I do not get out of bed											1
Patient is unresponsive											0
Thank you for your time											
Office Use:										Totals	
Date:	Treatment :			Cycle:		Day:

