2.2 Outline of the project

It is widely recognised that patient-reported outcomes give a measure of overall effect of clinicians' actions on patients and that they can be used to guide the management of the patient's condition (1-4). They can also have an empowering effect as the patient may feel that they are agents, and not just subjects, in their treatment pathway (5, 6). In the case of advanced and metastatic prostate cancer (i.e. cancer which has spread from the prostate to distant sites, the clinical means of assessing how the patient's disease is responding to treatment (Level of PSA [prostate specific antigen, produced normally in the prostate but also produced in prostate cancer cells], and radiological/magnetic scans) are somewhat imperfect as they do not take into account the impact on the patient's life and his response and reaction.

The Wolverhampton Assessment Tool (copy attached) is an objectively analysed, reproducible clinical assessment tool, developed from validated clinical study tools and piloted and refined with patient and clinician feedback to produce a simple 5-item questionnaire which asks patients how they feel normally in terms of pain, urinary frequency, eating, and tiredness. Patients are also asked to pick from a list the single statement which best represents them normally. The working hypothesis is that the patient's scores and his chosen statement correlate with the current state of his disease (7) and indicate whether the current treatment regimen needs clinician intervention.

The Tool allows assessment of the patient's disease status without him always needing to attend hospital and hence reduces potential exposure to Covid-19 for both patient and hospital staff. See attached *Oncology Interim Prostate Cancer Patient Management Guidelines* Royal Wolverhampton Hospital, March 2020 (8)

The aims of the present project are to:

- 1 evaluate how the Tool and the patient's clinical status correlate
- 2 examine patient and clinician attitudes to using the Tool

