- d) Level of PSA – prostate specific antigen, produced normally in the prostate but also produced in prostate cancer cells.
- e) Co-morbidities
- f) Current and previous treatments

The main outcome of the first phase will be to refine, as necessary, both the Tool and the research instruments as well as to establish proof of principle of the clinical utility of Tool.

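### Does the undefined 'Totals' box on the Tool's form, printed below items that run in opposite directions, undermine the planned analysis?

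*Protocol*

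**What the plan says.** Protocol section 2.2 describes a "simple 5-item questionnaire which asks patients how they feel normally in terms of pain, urinary frequency, eating, and tiredness". The next sentence adds, separately, the statement that the patient picks from a list. The form in section 2.8 scores each of the four symptoms from 0 (none) to "10 As bad as I can imagine". The activity statements carry 10 beside "I am fully completing my normal activities" and descend to 0 beside "Patient is unresponsive". Below them, in the office-use area, is a box headed 'Totals'. The form does not say which numbers go into it, whether the activity score is reversed, or how the result is read.

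The first research question (section 2.1) is "To what extent do each of the five items in the WAT correlate to the patient's disease status". The working hypothesis in section 2.2 names the patient's scores and his chosen statement as two things, and says that they "indicate whether the current treatment regimen needs clinician intervention". Section 2.3 presents the Tool "as a means of home monitoring of patients". Section 2.5 names rank methods (Mann-Whitney U, Spearman) and no composite score.

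**The concern.** A box headed 'Totals' under five numbered answers invites the reader to add all five. Four of them rise as the patient gets worse and one falls, so each point of lost function would take a point off a sum that otherwise rises with severity. Such a total could stand still or drop while a patient deteriorates on every item. Two members of staff could also fill the box differently from the same answers, one adding five numbers and the other adding the four symptoms.

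The form is the instrument under evaluation, and it is meant for monitoring patients away from the hospital. If anyone relied on that total, in the clinic or in an analysis, it would be a poor measure of disease status, and the error would be easy to miss.

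**Working it through.** The protocol states no total, so there is no figure of its own to reproduce. The inputs are the printed anchors in section 2.8: four symptoms scored 0 to 10 (higher worse) and activity scored 10 to 0 (higher better).

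**1. What a five-number sum would do.** Let S be the sum of the four symptoms and A the activity score. The printed sum is S + A. With activity reversed, the aligned sum is S + (10 − A).

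| Answers (four symptoms; activity) | S + A | S + (10 − A) |
|---|---|---|
| 0,0,0,0; 10 (best) | 10 | 0 |
| 0,0,0,0; 0 | 0 | 10 |
| 10,10,10,10; 0 (worst) | 40 | 50 |
| 10,10,10,10; 10 | 50 | 40 |
| 2,2,2,2; 9 | 17 | 9 |
| 3,3,3,3; 5 | 17 | 17 |
| 3,3,3,3; 4 | 16 | 18 |

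The last three rows show a tie and a reversal for patients who are worse on all five items. In general, when symptoms rise by D points and activity falls by e points, the printed sum changes by D − e. It ties when e = D and reverses when e > D.

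**2. How often that happens.** Take all ordered pairs of response patterns in which the second is no better on any item and worse on at least one. An 11-level item allows 66 such no-better orderings, so there are 66^5 − 11^5 = 1,252,332,576 − 161,051 = 1,252,171,525 pairs. Counting those with e > D gives 3.5% reversed, and those with e = D give 1.7% tied. About 95% keep their order. The aligned sum reverses and ties none. This gives every pattern equal weight, which is an assumption and not a figure from the protocol.

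**3. Whether a planned analysis uses such a sum.** Read together:
- Section 2.1 asks about each item.
- Section 2.2 keeps the scores and the statement apart.
- Section 2.5 lists rank methods and no composite.
- No section says that a total is analysed or acted upon.

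**4. What the opposite direction does to the analysis that is planned.** Replacing A by 10 − A reverses the ranks and nothing else. Spearman's coefficient with any measure Y satisfies ρ(10 − A, Y) = −ρ(A, Y). Likewise the Mann-Whitney statistic U becomes n₁n₂ − U. Size and two-sided p-value are unchanged. The activity item is simply expected to carry the opposite sign from the four symptoms, and its printed wording makes that plain.

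**The case for a change.** The strongest case for acting is that the box sits on a form filled in by hand, so a scoring rule written elsewhere would not label it. Section 2.2 calls the Tool reproducible, yet the box can be completed in more than one way. Later phases would carry the form to other hospitals and into an app.

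The 95% figure may also be kind. Successive forms from one patient may differ by only a point or two, and a fall in activity with no change in symptoms always lowers the printed sum.

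In an assumed one-factor model with equal loadings l, the correlation with severity is 3l/√(5 + 4l²) for the printed sum and 4l/√(4 + 12l²) for the four symptoms alone. At l = 0.5 these are 0.61 and 0.76; at l = 0.4 they are 0.51 and 0.66; at l = 0.7 they are 0.80 and 0.89. So adding activity unreversed would be worse than leaving it out.

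The arithmetic stands, and so does the ambiguity of the box. The step from there to harm does not. The loadings are assumed, and the five-number sum is only one possible reading: a symptom total with activity kept apart fits section 2.2 at least as well. A scoring rule may lie in an analysis plan or in the hospital guideline attached to the protocol, neither of which is at hand. Any reader of the form also sees each score and the activity statement in words, so a patient who is worse on every item is visibly worse whatever is written in the box.

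**Conclusion.** The concern describes the form correctly but does not reach the plan. Carried out as written, the item-by-item rank correlations are sound; the only consequence is the expected sign for the activity item. The possible misordering (3.5% of comparable pairs reversed and 1.7% tied, all patterns equally weighted) belongs to a five-number sum that the protocol never defines or uses.

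What remains is a missing label on an office-use box. An analyst would either ignore it or rebuild any total wanted from the item scores, so no information is lost. Section 2.3 already provides for tidying the form: "The main outcome of the first phase will be to refine, as necessary, both the Tool and the research instruments". The conclusion assumes that item scores are kept and that no decision rests on the total alone. Nothing in the protocol suggests otherwise. If a total were later made an analysis variable or a trigger for action, its scoring would have to be stated at that point.
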